3.6. Study Termination

The study will be terminated if the MTD is associated with insufficient drug exposure.

The study may be discontinued for any clinically significant changes, or pattern of changes (for example, clinically significant laboratory abnormalities), that are judged by the Investigator and/or Sponsor to be related to the study drug and represent a major tolerability concern.

The Principal Investigator reserves the right to terminate the study in the interest of subject safety and welfare. The Sponsor reserves the right to discontinue the study due to administrative reasons at any time.

4. SELECTION OF SUBJECTS

4.1. Healthy Subjects in Study Parts A, B, and C

Subjects must meet all of the inclusion criteria and none of the exclusion criteria to be eligible for the study.

***Criteria that are marked with an asterisk and in bold font also apply to subjects with CG and subjects with GALK-deficient Galactosemia.**

4.1.1. Inclusion Criteria

1. Healthy male or non-pregnant, non-lactating female subject between 18 and 65 years of age, inclusive.
2. ***Females must be of non-childbearing potential (defined as surgically sterile [i.e., had a bilateral tubal ligation, hysterectomy, or bilateral oophorectomy ≥6 months prior to the first dose of study drug] or postmenopausal for ≥1 year [confirmatory follicle-stimulating hormone or FSH test results required] prior to the first dose of study drug) or agree to use an acceptable form of birth control from screening until 30 days after study completion.**
3. ***Males must be unable to procreate (defined as surgically sterile [i.e., had a vasectomy ≥6 months prior to screening]) or must agree to use an acceptable form of birth control from screening through 30 days after study completion.**
4. No significant disease as determined by the Investigator during screening.
5. ***No clinically significant abnormal laboratory value as determined by the Investigator during screening.**
6. No significant abnormality on 12-lead ECG as determined by the Investigator during screening.
7. ***Subject's vital signs (measured after 5 minutes rest in a seated position) at screening must be within the following ranges: systolic blood pressure (SBP) <140 mmHg; diastolic blood pressure (DBP) <90 mmHg; and heart rate between 50 and 100 bpm, inclusive.**
8. No regular medical treatment outside of female birth control methods (females of childbearing potential only).
9. ***Able to communicate effectively with study personnel.**
10. ***Willing and able to be confined to the CRU as required by the protocol.**
11. Willing and able to give written informed consent after being informed of and understanding the nature of the study.

4.1.2. Exclusion Criteria

1. History or presence of clinically significant hematopoietic, renal (estimated glomerular filtration rate [eGFR] < 90 mL/min/1.73 m²), hepatic, endocrine, metabolic, pulmonary, neurological, psychiatric, cardiovascular, immunological, dermatological, or gastrointestinal

diseases; conditions capable of altering the absorption, metabolism, or elimination of drugs; or conditions that constitute a risk factor when taking the study drug and/or impact the conduct or results of the study.

2. ***Body Mass Index (BMI) $>35 \text{ kg/m}^2$.**
3. ***Underweight or BMI $< 17.5 \text{ kg/m}^2$.**
4. ***Positive test for hepatitis B surface antigen, hepatitis C antibody, or human immunodeficiency virus (HIV) at screening or previous treatment for hepatitis B, hepatitis C, or HIV infection.**
5. Evidence of significant active neuropsychiatric disease.
6. Has smoked or used tobacco- or nicotine-containing products ≤ 6 months prior to the first dose of study drug.
7. ***Pregnant, lactating, or not using/not willing to use appropriate means of contraception.**
8. ***Any prior history of substance abuse (including alcohol) or treatment for such.**
9. Positive urine screen for drugs of abuse (amphetamines, barbiturates, benzodiazepines, cocaine, cannabinoids, opiates) or cotinine.
10. ***History of significant drug allergy or drug hypersensitivity.**
11. ***Investigators, site personnel directly affiliated with this study, and their immediate families (defined as a spouse, parent, child, or sibling, whether biological or legally adopted).**
12. ***Any other condition that, in the opinion of the Investigator, precludes the subject from following and completing the protocol.**
13. A clinically significant abnormal finding on the physical exam, medical history, ECG, or clinical laboratory results at screening.
14. A significantly abnormal diet (per Investigator judgment) during the 4 weeks preceding the first dose of study drug.
15. ***Participation in another clinical trial of a different investigational product (randomized subjects only) within 5 half-lives prior to the first dose of study drug.**
16. Use of any over-the-counter (OTC) medication (including nutritional or dietary supplements, herbal preparations, or vitamins) ≤ 7 days prior to the first dose of study drug through the last dose of study drug without evaluation and approval by the Investigator.
17. Use of any prescription medication, except that allowed per protocol ([Section 4.6](#)), from 14 days prior to the first dose of study drug through the last dose of study drug without evaluation and approval by the Investigator.
18. ***Treatment with any sensitive substrates of Breast Cancer Resistance Protein (BCRP) (e.g., rosuvastatin, sulfasalazine) or potent inhibitors of BCRP (e.g., cyclosporine A) ≤ 5 half-lives days prior to the first dose of study drug through the last dose of study drug.**

19. *Treatment with sensitive substrates of Organic Anion Transporter (OAT)1 and OAT3 (e.g., famotidine, adefovir, furosemide, ganciclovir, cefaclor, ceftizoxime, pen-G) ≤ 5 half-lives prior to the first dose of study drug through the last dose of study drug.
20. *Treatment with sensitive substrates of cytochrome P450 3A4 (CYP3A4) (e.g. midazolam, triazolam, buspirone, alfentanil, dronedarone, eletriptan, conivaptan, lovastatin, simvastatin), or CYP2B6 (e.g. bupropion), or CYP2C19 (e.g. omeprazole), or CYP1A2 (e.g. alosetron, caffeine, duloxetine, melatonin, ramelteon, tasimelteon, tizanidine) ≤ 5 half-lives prior to the first dose of study drug through the last dose of study drug
21. *Consumption of beverages or foods that contain alcohol, high levels of sorbitol, grapefruit, poppy seeds, broccoli, Brussels sprouts, pomegranate, star fruit, char-grilled meat, or caffeine/xanthine from 48 hours prior to the first dose of study drug through the last dose of study drug. Subjects will be instructed not to consume any of the above products; however, allowance for an isolated single incidental consumption may be evaluated and approved by the Investigator based on the potential for interaction with the study drug.
22. *Treatment with medications potentially associated with transaminase elevations, such as mirtazapine ≤ 5 half-lives prior to the first dose of study drug through the last dose of study drug.

4.2. Subjects with Classic Galactosemia (CG) in Study Part D and Part D Extension

Subjects must meet all of the inclusion criteria and none of the exclusion criteria to be eligible for the study.

*Criteria in Section 4.1 that are marked with an asterisk and in bold font also apply to subjects with CG (Part D and Part D Extension).

4.2.1. Inclusion Criteria

1. Male or non-pregnant, non-lactating female subject between the ages of 18 and 65 years, inclusive, with a CG diagnosis confirmed by evidence of absent or significantly decreased ($<1\%$) GALT activity in red blood cells or historical record of diagnosis of GALT deficiency (medical record or gene analysis report or written communication by health care professional), and who have no other significant health problems.
2. Subject may be on concomitant medications and dietary supplements; however, they must be on stable doses for at least 1 month prior to screening and throughout the study.
3. Subject may have long-term complications of Galactosemia, including mild neurological deficits such as ataxia, tremor, dysmetria and dystonia, mild cognitive impairment, mild language difficulty, and primary ovarian insufficiency, that, in the opinion of the Investigator, do not interfere with the subject's ability to participate in the study.
4. Galactose-restricted diet that eliminates sources of galactose from dairy products but permits minimal dietary intake of galactose from non-dairy products for ≥ 3 months prior to screening and throughout the study.

5. Screening 12-lead ECG with normal sinus rhythm without pathological Q wave or significant ST/T wave changes.
6. Willing and able to consent voluntarily to participate in this study by providing written informed consent prior to the start of any study-specific procedures, with participation and consent of caregiver/LAR as well.

4.2.2. Exclusion Criteria

1. History or presence of clinically significant hematopoietic, hepatic, endocrine, metabolic (other than CG), pulmonary, neurological (other than CG-related), psychiatric, immunological, dermatological, or gastrointestinal diseases; conditions capable of altering the absorption, metabolism, or elimination of drugs; or conditions that constitute a risk factor when taking the study drug and/or impact the conduct or results of the study.
2. Evidence of diagnosis of clinical variant Galactosemia.
3. Complications of CG resulting in disability that, in the opinion of the Investigator, may prevent the subject from completing all study requirements (e.g., severe neurological deficits, severe cognitive impairment, or severe language difficulty).
4. Impaired renal function or eGFR < 90 mL/min/1.73 m², or urine protein-to-creatinine ratio (UPCR) ≥ 200 mg/g, or urine albumin-to- creatinine ratio (UACR) (≥ 30 mg/g. Note: eGFR and UPCR/UACR are an estimation of renal function, and the ultimate decision of whether a patient has normal renal function (and can be included in the study) is at the discretion of the Investigator, assuming there are no safety concerns. Also, because eGFR, UPCR and UACR can vary day to day based on outside factors, patients can be re-screened for eGFR, UPCR and UACR multiple times to understand the renal function of the patient.
5. History or presence of significant cardiovascular disorders including myocardial infarction, stroke, uncontrolled hypertension (sitting blood pressure ≥140/90 mmHg), left ventricular (LV) hypertrophy, atrial fibrillation, or valvular heart disease.
6. Abnormal findings on the screening 12-lead ECG, such as ST/T wave changes of ischemia, pathological Q wave changes, or any rhythm other than normal sinus rhythm.
7. Evidence of significant active hematological disease and/or cumulative blood donation of 1 unit (500 mL) or more including blood drawn during clinical studies in the last 3 months.
8. Unwilling to comply with a galactose-restricted diet.
9. Positive urine screen for drugs of abuse (amphetamines, barbiturates, benzodiazepines, cocaine, cannabinoids, opiates) unless clinically indicated.
10. Use of any OTC medication (including nutritional or dietary supplements, herbal preparations, or vitamins) ≤7 days prior to the first dose of study drug through the last dose of study drug without evaluation and approval by the Investigator. Use of medications to treat Galactosemia complications will be permitted by approval of the Investigator.
11. Use of any prescription medication, except that allowed per protocol ([Section 4.6](#)), from 14 days prior to the first dose of study drug through the last dose of study drug without evaluation and approval by the Investigator. Use of medications to treat Galactosemia complications will be permitted by approval of the Investigator.

12. For Part D Extension only, discontinuation due to study drug related TEAE in Part D.
13. Use of the following following potentially nephrotoxic drugs within 5 half-lives prior to the first dose of study drug through the last dose of study drug: amitriptyline, aspirin, doxepin, lithium, amphotericin B, foscarnet, ganciclovir, pentamidine, rifampin, antiretrovirals (e.g. adefovir, tenofovir), calcineurin inhibitors (e.g. cyclosporine, tacrolimus), angiotensin-converting enzyme inhibitors, angiotensin receptor blockers, clopidogrel, ticlopidine, pamidronate, zoledronate, statins, chemotherapeutics, contrast dye, loop diuretics, thiazides, triamterene, allopurinol, gold therapy, haloperidol, quinine, ranitidine.

4.3. Subjects with GALK-deficient Galactosemia in Study Part E

Subjects must meet all of the inclusion criteria and none of the exclusion criteria to be eligible for the study.

***Criteria in Section 4.1 that are marked with an asterisk and in bold font also apply to subjects with GALK-deficient Galactosemia (Part E).**

4.3.1. Inclusion Criteria

Same as for Part D except for Inclusion Criterion 1:

1. Male and non-pregnant, non-lactating female adult between the ages of 18 and 65 years, inclusive, with a GALK-deficient Galactosemia diagnosis documented by historical record of either absent or significantly decreased GALK activity in red blood cells (medical record, enzyme activity report, genetic mutation report or written communication by health care professional) and who have no other significant health problems.

4.3.2. Exclusion Criteria

Same as for Part D except that “GALK-deficient Galactosemia” replaces “CG” in Exclusion Criteria 1 and 3; and the exclusion criterion related to discontinuation from Part D does not apply.

4.4. Subject Participation in Multiple Cohorts

Subjects in Parts D and E may participate in multiple cohorts within the same study Part (assuming no safety or tolerability issues in the prior cohort) regardless of whether they are treated with AT-007 or placebo in any cohort. However, there must be a washout period ≥ 5 days between the last dose of study drug in a cohort and the first dose of study drug in the next cohort. Subject who participates in multiple cohorts must consent to each cohort separately.

Subjects in Part D may participate in Part D Extension (separate consent required) regardless of whether they completed Part D or not as long as Part D discontinuation was not due to a study drug related TEAE. The timing from the end of Part D to the start of Part D Extension is addressed in [Section 3.3.6](#). A screening visit is required for subjects whose last visit in Part D was >60 days before Day 1 in the Part D Extension. However, some screening procedures done before Part D do not need to be repeated.

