The 90-day Part D Extension (separate informed consent required) is open for subjects with CG who completed Part D, participated in but did not complete Part D for reasons other than study drug related treatment emergent adverse event (related TEAE), or did not participate in Part D. Subjects who previously completed Part D may participate in the 90-day Extension at any time after the EOS Visit (scheduled for 28 days after the last dose in Part D MAD). Subjects who participated in but did not complete Part D may participate in the Extension after either the EOS Visit (if they have this visit and it occurs beyond 14 days after the last dose) or a minimum 2-week wash-out period after the last dose received in Part D (if they do not have the EOS Visit or have it before 2 weeks after the last dose).

Subjects with CG who have not previously participated in Part D may be prescreened (optional) and participate in the 90-day Extension after they undergo all the required screening procedures from Day -60 to Day -1. Subjects with last visit in Part D more than 60 days before Day 1 in Part D Extension will also need a screening visit although some screening procedures done before Part D do not need to be repeated. Subjects in the Part D Extension will be randomized in a 3:1 ratio to active drug at the daily dose of 20 mg/kg or placebo. Most doses during the Part D Extension will be taken at home, but there are 2 in-clinic stays. A second cohort may be initiated in the Part D Extension to evaluate a dose higher than 20 mg/kg/day. If so, subjects will be randomized in a 3:1 ratio to active drug or placebo and will take most doses at home, except for 2 in-clinic stays. Also, subjects in Part D Extension will have blood samples collected for both PK and biomarkers of galactose metabolism.

The starting dose in Part A was 0.5 mg/kg as a single dose. Subsequent doses in Part A and all doses in Parts B, C, D, and E are based on the results of previous cohorts and/or previous parts of the study.

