One to 3 dosing cohort are planned for subjects with GALK-deficient Galactosemia (Part E). The same subjects will receive both the single dose and the multiple doses. Within each cohort of 6 subjects, 4 subjects will be randomly assigned to AT-007 and 2 subjects will be randomly assigned to placebo. Following a single dose of study drug (AT-007 or placebo), there will be a 5-day washout. Subjects who tolerate the single-dose will receive 1 daily dose of the same study drug (AT-007 or placebo) for 27 consecutive days. The decision of whether each individual subject can start multiple dosing will be made by the Investigator in consultation with the Sponsor. **No subject in Part E can start multiple dosing without explicit agreement from the Sponsor.** Subjects will complete the 27 days of treatment and the associated PK, PD, and safety assessments through the 2 days after the MAD portion and then have an EOS Visit at 28 days after the last dose.

Notes for Parts D and E: The overall number of subjects per cohort may be increased up to 8 subjects to address any potential lost-to-follow-up among subjects treated with either placebo or AT-007. Subjects treated with study drug (placebo or AT-007) in a cohort may be randomized to treatment in another cohort (separate consent required) within the same Part (assuming no safety or tolerability issues in the prior cohort) as long as there is a washout period of ≥ 5 days between the last dose in a cohort and the first dose in the next cohort.

The dose for the first cohort of the Part D Extension (DE1) will be 20 mg/kg/day based on acceptable SAD and MAD safety and PK data from Cohort D2. After SRC review of all SAD and MAD data and Sponsor review of PK and galactitol data for Cohorts D1 through D3, a second cohort of the Part D Extension (DE2) may be initiated to evaluate a dose >20 mg/kg/day if this dose was well tolerated in the SAD and MAD portions of the study in both healthy volunteers and subjects with CG.

In Part D Extension, within each cohort of up to 28 subjects, subjects will be randomly assigned in a 3:1 to AT-007 and placebo. Subjects will receive 1 daily dose of the same study drug (AT-007 or placebo) for 90 consecutive days. Subjects will complete the 90 days of treatment

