3.2. Rationale for Overall Study Design

The overall study design is commonly used for Phase 1 safety and PK studies. Incorporation of sentinel subjects in any cohort, especially the first cohort, is designed to limit the number of subjects exposed to a potentially unsafe drug or unsafe dose. The durations of the in-clinic stays are based on safety and practical considerations to ensure proper assessment of potential AEs and collection of biological samples and various examinations/measurements required by the study. An EOS or EOE Visit is conducted at 28 days after the last dose to assess the outcome of AEs (if any) after study drug treatment and to ensure proper reporting of AEs with onset during the post-treatment period. Use of an SRC to assess safety and PK data before dose escalation and before transitioning from single doses (Part A) to multiple doses (Parts B and C) is standard practice in such studies. Having safety and PK data in healthy subjects before dosing subjects with the proposed indication(s) (Parts D, E, and D Extension) is also standard practice. Having longer duration doses not exceed doses that have been studied for shorter durations is standard practice as well. Having the Investigator (with explicit agreement from the Sponsor) rather than the SRC decide if safety for the sentinel subjects in Cohort A1 is acceptable and if a subject in Part D or E will start multiple dosing with study drug after the single dose are practical consideration because the decisions needs to be made within 24 hours (Cohort A1) and within the 5-day washout period (individual subjects in Parts D and E). Galactose and its metabolites are only measured in subjects with CG or GALK-deficient Galactosemia (Parts D, E, and D Extension) because AR (the enzyme inhibited by AT-007) converts galactose to galactitol only in the presence of extremely high levels of galactose (found in subjects with CG or GALK-deficient Galactosemia but not healthy subjects).

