3.3.6. Part D Extension: 90-Day Dosing in Subjects with Classic Galactosemia

The Part D Extension is open to the following subjects:

- Subjects who completed Part D may start in the extension at any time after the EOS Visit in Part D.
- Subjects who participated in but discontinued Part D for reasons other than study drug related TEAE (and completed an EOS Visit at any time >14 days after the last dose) may start in the extension at any time after the EOS Visit in Part D.
- Subjects who participated in but discontinued Part D for reasons other than study drug related TEAE (and who either did not have an EOS Visit or had an EOS Visit before 14 days after the last dose) may start in the extension at any time beyond 14 days after the last dose in Part D.
- De novo subjects who did not participate in Part D may participate in the 90-day Extension after they undergo all the required screening procedures from Day -60 to Day -1.

The dose for the first cohort of the Part D Extension (DE1) will be 20 mg/kg/day based on acceptable SAD and MAD safety and PK data from Cohort D2. After SRC review of all SAD and MAD data and Sponsor review of PK and galactitol data for Cohorts D1 through D3, a second cohort of the Part D Extension (DE2) may be initiated to evaluate a dose >20 mg/kg/day if this dose was well tolerated in the SAD and MAD portions of the study in both healthy volunteers and subjects with CG.

A screening visit is required for de novo subjects and subjects whose last visit in Part D was >60 days before Day 1 in the Part D Extension. The de novo subjects may also participate in optional prescreening.

Within each cohort of up to 28 subjects, subjects will be randomly assigned in a 3:1 to AT-007 and placebo. Subjects will receive study drug (AT-007 or placebo) on Day 1 and remain at the CRU for at least 24 hours after the first dose. Subjects will receive 1 daily dose of the same study drug (AT-007 or placebo) for a total of 90 consecutive days. In the extension, subjects will take most of their doses at home (fasting conditions [[Section 5.3](#)] recommended). Subjects will have

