6.7.9. Day 34 (Discharge from Third In-clinic Period)

The following procedures will be done:

- Collect postdose blood sample for PK

- Collect postdose blood sample for analysis of biomarkers of galactose metabolism including galactose, galactitol, and galactose-1-p
- Perform physical examination including weight
- Measure vital signs
- Collect AE and concomitant medications data
- Schedule the EOS Visit for Day 60 (± 2 days)
- Discharge subject from the CRU and remind subject/caregiver to fast overnight for at least 10 hours on the day before the EOS Visit and return to the CRU for the EOS Visit before breaking the fast

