6.9. EOS or EOE Visit (28 Days After the Last Dose)

All subjects will return to the CRU for an out-patient EOS Visit at 28 ± 2 days (Part A [Day 28]; Parts B and C [Day 35]; Parts D and E [Day 60];) after the last dose. For the Part D Extension, the EOE Visit (Day 118 ± 2 days) can be done either as a home health visit or as an out-patient visit to the site. The EOE Visit will not be performed if subjects transition to the separate Open-

Label Extension Study. The study completion for these subjects will be the completion of the Treatment Period at Day 91. The following procedures will be done:

- Update medical history (including current medications)
- Perform physical examination including weight
- Collect fasting blood sample(s) for clinical laboratory testing (hematology, coagulation and biochemistry); and, for female subjects of childbearing potential only, serum pregnancy test
- Collect fasting urine sample for urinalysis, UACR and UPCR
- Measure vital signs
- Conduct 12-lead ECG
- Collect AE and concomitant medication data

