7.12.2 Adverse Events

All AEs will be coded to system organ class (SOC) and preferred term (PT) using MedDRA, Version 22.0 or later, and presented by subject data listings.

A treatment-emergent AE (TEAE) is defined as an AE that is not present prior to cohort with investigational product, but appeared following cohort or was present at cohort initiation but worsened during cohort. An AE that was present at cohort initiation but resolved and then

reappeared while the subject was on cohort is a TEAE (regardless of the intensity of the AE when the cohort was initiated). Programmatically, an AE will be classified as a TEAE if the start date and time occurs on or after the start date and time of first investigational product dosing.

The TEAE will be assigned to treatment based on the start date/time of occurrence.

The overall incidence of TEAEs (number and percentage of subjects) as well as the number of events will be summarized by cohort, severity grade, SAEs, causally related TEAE and SAEs, TEAEs leading to study or treatment discontinuation, life-threatening SAEs, and SAEs resulting in death.

The TEAEs will be summarized and tabulated at both the subject (number [%] of subjects) and event (number of events) level:

- By cohort, SOC, and PT
- By cohort, SOC, PT, and maximum reported severity
- By cohort, SOC, PT, and closest relationship to study drug

For the incidence at the subject level by SOC and PT, if a subject experiences more than 1 event within the same SOC and PT, only 1 occurrence will be included in the incidence.

For the incidence at the subject level by SOC, PT, and severity, if a subject experiences more than 1 event within the same SOC and PT, only the highest severity grade will be included in the incidence.

For the incidence at the subject level by SOC, PT and relationship to study drug; if a subject experiences more than 1 event within the same SOC and PT, only the most closely related occurrence will be included in the incidence.

Any SAEs, AEs with outcome of deaths, or AEs resulting in discontinuation of study or cohort will be presented.

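### In Part D and E subjects re-dosed within 28 days, SAP 7.12.2 counts a late AT-007 adverse event only under the new assignment, because it has no carry-over window

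*Protocol*

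**What the plan says.** **Re-entry.** Protocol Section 4.4 allows subjects in Parts D and E to take part in more than one cohort of the same part, whichever treatment they had before. The timing condition is that "there must be a washout period ≥ 5 days between the last dose of study drug in a cohort and the first dose" given after re-randomization. The other conditions are a separate consent and no safety or tolerability issue in the prior cohort. The rule recurs in Protocol Sections 3.1, 3.3.4, 3.3.5, 5.2 and 9.1 and in SAP 3.1.4.4, 3.1.4.5 and 7.13. None of these places requires the earlier cohort's EOS visit first.

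**Extension.** Part D completers may enter only after their EOS visit. Section 3.3.6 gives a shorter route to subjects who left Part D for a reason other than a related TEAE and had no EOS visit, or an early one. They "may start in the extension at any time beyond 14 days after the last dose in Part D".

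**Follow-up.** Section 6.9 states: "All subjects will return to the CRU for an out-patient EOS Visit at 28 ± 2 days" after the last dose, which is Day 60 in Parts D and E. Section 3.2 gives one purpose of the visit as "to ensure proper reporting of AEs with onset during the post-treatment period".

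**Analysis.** SAP 7.12.2 states: "The TEAE will be assigned to treatment based on the start date/time of occurrence". A TEAE is any event starting on or after first dosing. No upper limit, lag or rule for re-dosed subjects is given. SAP 7.12.1 summarizes safety by cohort, pooled AT-007 and pooled placebo within each part. SAP 7.1 puts Part D and the Extension in separate output sets.

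**The concern.** Safety is the primary endpoint. The protocol treats the 28 days after the last dose as time in which an event from that treatment may still appear. The re-entry rule allows a new random assignment inside that time, and the SAP then gives every later event to the new assignment.

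An event that belongs to AT-007 could thus be counted under placebo, or an event from one dose level under another. For a Part D discontinuer in the Extension, it would move to a different set of outputs. The bar on earlier safety or tolerability issues cannot screen out an event that has not yet appeared.

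The SAP does handle carry-over for pharmacokinetics: Section 6.1.2 drops a subject's parameters from the summaries if the Day 1 predose concentration exceeds 5% of Cmax. It has no counterpart for adverse events.

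**Working it through.** **Inputs.** Last dose in Parts D and E on Day 32 (Protocol 3.3.4, 3.3.5). EOS visit at 28 ± 2 days (6.9). Minimum gap of 5 days between cohorts (4.4) and beyond 14 days for the discontinuers (3.3.6). Multiple dosing starts on Day 6. Allocation is 4:2 within a Part D or E cohort and 3:1 in the Extension.

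**The plan's own figures.** 32 + 28 = Day 60, as stated. 90 + 28 = Day 118 for the Extension, as stated. 40 + 32 + 28 = 100 days maximum participation in Part D, as stated.

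**Re-entry at the 5-day minimum.**
- The earliest new first dose is 32 + 5 = Day 37, which is Day 1 of the next cohort.
- The old Day 60 becomes 60 − 37 + 1 = Day 24 of the next cohort. That is the 24 − 6 + 1 = 19th daily dose of its multiple-dose period.
- Follow-up days under the new assignment: 28 − 5 = 23, and 23/28 = 82%. With the ± 2-day visit window the range is 21 to 25 days.

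**Extension entry just beyond 14 days.** At most 28 − 14 = 14 days (50%) fall under the new assignment. If the first dose is on day 15, it is 28 − 15 = 13 days (46%).

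**Longer gaps.** The number of affected days is 28 minus the gap, and it is zero once the subject has waited 28 days.

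**Possible sequences**, assuming the planned 4:2 allocation in both cohorts and independent assignments:

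| First, then second | Share of re-entrants | Effect on a late AT-007 event |
|---|---|---|
| AT-007, placebo | 4/6 × 2/6 = 22% | counted under placebo |
| AT-007, AT-007 | 4/6 × 4/6 = 44% | stays in pooled AT-007, may change dose level |
| Placebo, AT-007 | 2/6 × 4/6 = 22% | none |
| Placebo, placebo | 2/6 × 2/6 = 11% | none |

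For a Part D discontinuer, AT-007 followed by placebo in the Extension has probability 4/6 × 1/4 = 17%.

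**Where this can still happen.** The note to Table 5 describes Cohorts D1 and D2 as completed, and D3 waits for B4 (3.4). Part E may have one to three cohorts. E2 can open after safety review of E1 through Day 12 and Sponsor review of single-dose PK and galactitol (3.4). At that point E1 subjects may still be dosing or in follow-up. The open cases are therefore mainly E1 to E2 to E3, any added cohort, and the discontinuers entering the Extension.

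**The case against.** The strongest reply has four parts.

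1. **Five days is a minimum, not a schedule.** Re-entry needs a new consent, and Appendix E lists screening and a Day -1 check-in with no stated exemption for re-entrants. The subject is discharged on Day 34, and Day -1 for a Day 37 dose is Day 36. This stands: 82% is the extreme case, and typical gaps may be longer.

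2. **Safety checks precede re-dosing.** Section 6.3 sets an eligibility review, examination, vital signs, ECG, laboratory tests and AE collection on Day -1. Subjects with earlier safety or tolerability issues are excluded. This largely stands. At the minimum gap, however, Day -1 is only 4 days after the last dose. Section 6.3 also waives the laboratory tests if they were done at screening within 60 days, while Appendix E requires them on Day -1 regardless.

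3. **The consequence is tabulation only.** AE collection continues in the next cohort, by-subject listings are planned, the investigator judges causality, and the dose-limiting toxicity rule for the earlier cohort ends 24 hours after its last dose. This stands. A reader might infer that post-treatment events are lost, and the documents do not support that.

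4. **Onset-date assignment is clear and prespecified.** An event on the 19th daily dose of new AT-007 may well belong to the new course, so moving it to the old one could mislabel it. This stands, and it is why the main analysis should not change.

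A reader might also infer a large bias. With two Part E cohorts (8 on AT-007, 4 on placebo, each assignment counted once), one moved event changes the gap between the pooled rates by 1/8 + 1/4 = 37.5 points. With three cohorts (12 and 6) the figure is 1/12 + 1/6 = 25 points. The SAP plans no such difference and applies no inference to safety. The size comes mostly from the small placebo groups. It also needs a delayed AT-007 event, re-entry inside 28 days, the AT-007-then-placebo sequence, and no earlier occurrence of the same preferred term on AT-007.

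**Conclusion.** The gap is real but minor. The plan allows re-dosing before the 28-day visit, and it has no analysis that shows where a late event would fall if the previous treatment were held responsible. For a re-dosed subject, between 0 and 23 of the 28 follow-up days (up to 25 with the visit window) are attributed only to the new assignment. For the Part D discontinuers entering the Extension, the upper limit is about 14 days.

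This rests on re-entry inside 28 days actually occurring. The documents give neither the number of re-entrants nor their gaps. They also give no half-life. If it were 12, 24 or 48 hours (an assumption), 0.1%, 3.1% or 17.7% of the drug would remain after 5 days, from 0.5 to the power 120/half-life. A delayed hepatic or renal event need not depend on residual drug alone.

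A reader might conclude that the 5-day rule must be replaced by a wait for the EOS visit. The documents do not settle that. The wait is already required of Part D completers entering the Extension, but between cohorts it could delay recruitment in a rare disease. The Sponsor should weigh it as an option.

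**What to change.** Keep assignment by onset date as the main analysis. Add to SAP 7.12.2, and to the table list in Section 8, one supplementary TEAE table for subjects dosed in more than one cohort of Part D or E, or in both Part D and the Extension. In that table, an AE with onset within 28 days of the previous treatment's last dose is also counted under that previous treatment. Flag the same events in the AE listings. Subjects already re-dosed are covered, because the dates are collected. For subjects in both Part D and the Extension, the table can go with the Extension outputs, which SAP Section 4 reports as an addendum.

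The cost is one table and one flag. Some events will appear under two treatments, so a footnote should say that the columns are not additive.

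The Sponsor may also consider requiring the EOS visit before any further dosing. That adds no visit or test. It could add up to 23 days of waiting per re-entrant, and about 13 to 14 days per affected Part D discontinuer.
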